To enhance generalizability, we have designed a multicenter study in varying geographical regions within the US, involving patients who tested positive and are not in need of hospitalization. Using a randomized phase III clinical trial design, we will enroll 1500 COVID-19 positive patients who are not hospitalized, to be randomized to receiving 2 tablespoons (~20 grams) of resistant potato starch (RPS) twice daily for 14 days vs. placebo (2 tablespoons of non-resistant, digestible starch twice daily). We will evaluate the relationship between RPS and the primary outcome of hospitalization and the secondary outcomes of time to clinical recovery (TTCR) defined as return to normal body temperature, and alleviation of major presenting symptoms (myalgia, cough, shortness of breath, and GI symptoms) maintained for 72 hours and peak symptom severity score adapted from the influenza literature (2).

The dietary starch produced by Bob's Red Mill® is a commercially available low-digestible carbohydrate. It is entirely plant based and not genetically modified. It is gluten free. Potato-based starch contains 40 calories per 12 grams and no additional dietary nutrients, vitamins or sodium (labeling information). Corn-based starch contains 30 calories per 8 grams and no additional nutrients, vitamins or sodium (labeling information).

[figure not shown]
Starch has been well studied within the dietary and nutritional literature and has been demonstrated safe. (3-5). In addition, it has previously been administered to healthy human volunteers at the University of Michigan as part of HUM00118951 and HUM00094242– Linking the Structure and Function of the Gut Microbiome. These studies have revealed minimal adverse events and no serious adverse events in these subjects.

Moreover, it is being administered to allogeneic hematopoietic cell transplant (allo HCT) patients at the University of Michigan as part of HUM00112318 under IND 132208- Dietary manipulation of the microbiome-metabolomic axis for mitigating graft versus host disease (GVHD) in allo HCT patients. This study has revealed minimal adverse events and no serious adverse events in these subjects.

**Probable Duration of Project:** State the expected duration of the project, including all follow-up and data analysis activities. We anticipate a 12-month study duration, whereby the first six months will focus on RPS administration and data collection and the remaining six months on analysis and manuscript generation.

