### **Safety and Tolerability**

Analyses will be performed for all subjects having received at least one dose of study drug.

*Assessment of adverse events (**outlined in Table 3 above**)*

Every 2-day phone questionnaires (**Table 4**) and EHR review for the first 14 days followed by once weekly to complete a month follow up from last dose of treatment. Subjects will be followed for adverse events for at least 30 days after the last dose of study treatment. Subjects removed from treatment for persistent adverse events thought to be due to interventional treatment will be followed until resolution or stabilization of the adverse event.

**Table 4:** Time and Events

|                                   | Pre-Study  | Treatment Period/
Phone follow-up
(14 days) |                          | Follow-Up Period with phone and
electronic medical record (EHR) review |                         |                       |                       |
|-----------------------------------|------------|---|--------------------------|---|-------------------------|-----------------------|-----------------------|
| Observations                      | Enrollment | Day 1-14  | Every 2 days
day 0-14 | Every 7 days
through Day
30 from last
dose of
treatment       | Day 60
+/- 7
days | Day +90
+/- 7 days | Day 120
+/- 7 days |
| Informed
Consent
(phone)    | X          |   |                          |   |                         |                       |                       |
| Assessment of
co-morbidities   | X          |   |                          |   |                         |                       |                       |
| Study Agent                       |            | X   | X                        |   |                         |                       |                       |
| Side Effects                      | X          |   | X                        | X   |                         |                       |                       |
| Phone
Symptom
Questionnaire |            |   | X                        | X   |                         |                       |                       |
| Assessment of
medication use   | X          |   | X                        |   |                         |                       |                       |
| Assessment of
Hospitalization  |            |   | X                        | X   |                         |                       |                       |

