For our secondary outcomes, assuming a TTCA of about 14 days in the placebo group with standard deviation of 5 days, we calculated that a sample size of 196 would be required to provide 80% power (with a two-sided alpha level of 0.05) to detect an absolute reduction in TTCA by 2 days or more in the RPS group. For the outcomes of symptom severity score, we assumed that the placebo group would have a peak score of 20 with a standard deviation of 5 points, and we calculated that a sample size of 32 patients would be required to provide 80% power (with a two-sided alpha level of 0.05) to detect an absolute reduction in symptom severity score of 5 points or more in the RPS group.

Total accrual between all sites is 1500 patients. Depending on accrual rates, some sites may accrue more than other sites with a total goal of 1500 patients.

**Data analysis plan:** The primary outcome of hospital admission rates will be compared with the use of Pearson's chi-square test. The secondary outcomes of TTCA and symptom severity score will be compared in the two groups by means of a two-sample t-test. Adjusted measures and subgroup effects for the primary and secondary outcomes will be analyzed with the use of logistic regression and linear regression, respectively. Generalized estimating equations and linear mixed models will be used to test for an interaction between treatment group and

site in primary and secondary outcomes, respectively. The alpha level will be set at 0.05 for all analyses, 95% confidence intervals will be calculated, and all comparisons will be two-tailed.

*Interim analysis plans:*

Once our enrollment target for the secondary outcomes is reached (n~200), we will perform an interim analysis to assess safety, feasibility and treatment effect.

*Interim analysis 1(safety):*

All adverse events will be summarized and the independent data safety monitoring committee (DSMC) will make recommendations regarding continuation of recruitment. None of the DSMC members will be on our IRB protocol or the study team.

*Interim analysis 2 (feasibility):*

Study enrollment, follow up and any withdrawals from the study will be summarized and discussed by IDSMC to see if the degree of missing data is acceptable and if any further efforts need to be taken to optimize enrollment and follow up. Successful feasibility will be defined as more than 60% of patients took at least 50% of their prescribed doses (as directed by study team).

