**A. Over the past 2-3 days:**

|  | Absent | Mild | Moderate | Severe |
|--|--------|------|----------|--------|
| 1) Do you have loss of taste or smell?                       |        |      |          |        |
| 2) Do you have any bellyaches, diarrhea, or nausea/vomiting? |        |      |          |        |
| 3) Do you have a cough?                                      |        |      |          |        |
| 4) Are you short of breath or wheezy on rest or exertion?    |        |      |          |        |
| 5) Do you have a fever or feel feverish?                     |        |      |          |        |
| 6) Are you experiencing fatigue?                             |        |      |          |        |
| 7) Do you have a headache?                                   |        |      |          |        |
| 8) Do you have muscle aches, pains, or cramps?               |        |      |          |        |

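### The main test of the symptom severity score adjusts for neither day-0 score nor site, and the peak has no defined window, so a pre-treatment value can set it and shrink the estimated difference

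*Combined protocol and SAP*

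**What the plan says.** The main comparison is in Section 14, Data analysis plan: "The secondary outcomes of TTCA and symptom severity score will be compared in the two groups by means of a two-sample t-test". The next sentence adds: "Adjusted measures and subgroup effects for the primary and secondary outcomes will be analyzed with the use of logistic regression and linear regression, respectively". It lists no covariates. Site enters only through a separate test of treatment-by-site interaction, although the Randomization section stratifies by site.

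That the outcome is a peak appears in two places. Section 1 names the "peak symptom severity score adapted from the influenza literature", and the sample-size text in Section 14 says "we assumed that the placebo group would have a peak score of 20 with a standard deviation of 5 points". The outcome definition in Section 4 gives only the sum of eight items, range 0 to 24. It mentions neither a peak nor a baseline, and it counts calls from the start of treatment.

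Table 4 ticks the symptom questionnaire under "Every 2 days day 0-14" and not under Enrollment. The study agent is ticked for Day 1-14 and also in that same every-two-days column. Appendix A words the symptom questions as "Over the past 2-3 days".

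**The concern.** There are two gaps in one secondary outcome.

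The first is the undefined window. If the day-0 call counts toward the peak, a participant whose worst report is at day 0 contributes a value fixed before treatment. Participants enter only after a positive test, a phone approach, electronic consent and home delivery, so some may already be past their worst day. Their peaks would be the same on either starch. The resulting attenuation does not shrink with sample size: a large trial would estimate the diluted difference precisely.

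The second is the unadjusted main test. A score taken before the first dose is likely to predict the later peak, and using it would narrow the interval at little cost. With covariates unnamed, the choice of model stays open until the data are in hand. The score is also analysed at the interim look at about 200 patients, for efficacy and for harm, where precision is lowest.

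**Working it through.** **The plan's own figure.** The inputs from Section 14 are SD 5, difference 5, two-sided alpha 0.05 and power 80%. Allocation is not stated; 1:1 is assumed. Per arm, n = 2(1.960 + 0.842)² × 5²/5² = 15.7, so 16 per arm and 32 in total. This reproduces the plan: "a sample size of 32 patients would be required to provide 80% power". The t-based calculation gives 17 per arm (34 in total), with 78.1% power at 32.

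**Precision.** With correlation ρ between day-0 score and peak (assumed 0.3 to 0.7), the residual variance is 5²(1 − ρ²).

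| ρ | 1 − ρ² | residual SD | total N for 5 points |
|---|---|---|---|
| 0.3 | 0.91 | 4.77 | 30 |
| 0.5 | 0.75 | 4.33 | 24 |
| 0.7 | 0.51 | 3.57 | 18 |

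The difference detectable with 80% power is SD × 2.802 × √(4/N). At N = 200 it falls from 1.98 (SD 5) to 1.72 (SD 4.33). At 1500 × 0.9 = 1350 evaluable it falls from 0.76 to 0.66.

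**Attenuation.** Let B be the day-0 score and P the post-baseline peak, bivariate normal, each with SD 5. Take the mean of P as 20 on placebo and 15 on active, so the true effect is 5. If day 0 counts, the outcome is max(B, P). Its mean is the mean of P plus θ·g(a), where θ = 5√(2(1 − ρ)), a = (mean P − mean B)/θ and g(a) = φ(a) − aΦ(−a). At ρ = 0.5, θ = 5, and the observed difference is 5 − 5[g(a active) − g(a placebo)]. The day-0 mean is assumed.

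| day-0 mean | a placebo, g | a active, g | observed difference | N for 80% | power at 32 |
|---|---|---|---|---|---|
| 10 | 2.0, 0.0085 | 1.0, 0.0833 | 4.6 | 38 | 74% |
| 12 | 1.6, 0.0232 | 0.6, 0.1687 | 4.3 | 42 | 69% |
| 15 | 1.0, 0.0833 | 0.0, 0.3989 | 3.4 | 62 | 52% |
| 18 | 0.4, 0.2304 | −0.6, 0.7687 | 2.3 | 130 | 28% |

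The last two columns are t-based and use simulated SDs of the maximum: 4.87, 4.79, 4.68 and 4.65. The simulation gives the same differences. Across ρ from 0.3 to 0.7 the observed difference is 4.5 to 4.8 at a day-0 mean of 10, 3.3 to 3.6 at 15, and about 2.3 at 18. Rounding scores and cutting them off at 0 and 24 lowers the post-baseline difference itself to 4.47. At ρ = 0.5 the observed values are then 4.10, 3.75, 2.92 and 1.87, a similar proportional loss.

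**Power at the sizes actually planned.** Without adjustment, power for 5 points is about 100% at 200 and at 1350. For a halved effect of 2.5 points it is about 94% at 200 and about 100% at 1350.

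**Recall.** If the first dose falls on day 1 and recall reaches back three days, a day-2 call reaches day 2 − 3 = −1, before treatment. A day-4 call reaches day 4 − 3 = 1.

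**The case against.** The strongest reply is that the t-test is valid under randomisation. With no treatment effect, a day-0 value enters the peak alike in both arms, so the type I error is not inflated. The outcome is secondary, needs 32 patients by the plan's reckoning and will have far more. At ρ = 0.5 adjustment moves the detectable difference by only 0.10 points at 1350, on a 24-point scale. All of this stands. It limits the point to the estimate, its interval and the outcome definition.

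Three stronger readings are tempting, and the documents do not support them.

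- A reader might infer that the plan ignores covariates altogether. It does not: adjusted linear regression is planned for the secondary outcomes. What is missing is the covariate list and its standing as the main analysis.
- A reader might take day 0 as a documented pre-treatment baseline. That is an inference. Table 4 ticks no questionnaire at Enrollment, shows study agent in the same column as the calls, and Section 4 counts calls from the start of treatment. The first call could follow the first dose.
- A reader might infer that counting day 0 typically halves the effect. In the model above that needs a day-0 mean of about 18, close to the assumed placebo peak. At a day-0 mean of 10 the loss is 4% to 11%.

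**Conclusion.** The point holds for the outcome definition and the choice of main analysis, and it should be addressed. Nothing in the documents stops a pre-treatment score from setting the peak, and the direction of the resulting bias is toward no difference. Its size cannot be fixed from the documents: under the model used it runs from under half a point to more than half of a 5-point effect, depending mainly on how close the day-0 mean lies to the later peak. The precision forgone likewise depends on an assumed correlation. Neither gap threatens power for the planned 5 points or the validity of the test. The gain from correcting them is a less attenuated estimate, a narrower interval and an outcome fixed before unblinding.

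**What to change.** 1. In Section 14, make linear regression on treatment, day-0 score and site the main analysis of the symptom severity score, and keep the t-test as supportive.
2. In Section 4 and Table 4, state that the day-0 questionnaire is completed before the first dose.
3. Define the outcome as the maximum score over named calls after the first dose. Choose the first eligible call so that its whole recall period falls after that dose. Simply starting at day 2 may not achieve this, so the day-2 call may have to be excluded.

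The cost is a few lines of text and slightly more analysis work. Day 0 already appears in the call schedule, so no extra visit is foreseen. If, in practice, the first call now follows the first dose, the timing of that call must change as well as the wording. The stated sample size need not change.

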## Stopping Rules

During the interim statistical analysis, we will analyze the efficacy of RPS in relation to the primary outcome of hospitalization. If there is a significant difference between the two arms with p-value of <0.01, we will not continue the study.

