We will analyze the efficacy of RPS in relation to the primary outcome of hospitalization. If there is a significant difference between the two arm with p-value of <0.01, we will not continue the study. For data quality and integrity, we will also analyze the efficacy of RPS in relation to the secondary outcomes of TTCA and symptom severity score to assess efficacy and ensure no increase in harm in the intervention arm.

**Section 14. Statistical Considerations:** Describe the statistical analyses that support the study design.

**Study design/Study outcomes measures:** We will conduct a double-blinded, randomized clinical trial comparing RPS (~20g twice daily for 14 days) with placebo (non-resistant starch) in 1500 adults (age  $\geq 18$  years old) with COVID-19 diagnosis (defined by a positive swab) who are being managed in the outpatient setting. The primary outcome is hospital admission due to COVID-19 related complications. The secondary outcomes are TTCA and symptom severity score. We also will investigate some exploratory outcomes such as ER visits without admission, and among those hospitalized, we will explore differences in oxygen requirement, need for mechanical ventilation, duration of ventilation, length of hospital stay, levels of inflammatory markers routinely ordered as part of clinical care (CRP, LDH, D-dimer, Ferritin, IL-6), and rates of discharge between the RPS and placebo arms.

**Sample size and accrual:** Assuming a 14% admission rate in the placebo group, we calculated that a sample size of 1362 (we will enroll 1500 to account for 10% loss to follow up) will be required to provide 80% power (with a two-sided alpha level of 0.04 to detect an absolute reduction in hospital admission rates of 5% or more in the RPS group. **The primary analysis will be based on the intention-to-treat principle, with all patients included in their assigned group.**

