*Interim analysis 3 (treatment effect):*

We will analyze the efficacy of RPS in relation to the primary outcome of hospitalization. If there is a significant difference between the two arm with p-value of <0.01, we will not continue the study. For data quality and integrity, we will also analyze the efficacy of RPS in relation to the secondary outcomes of TTCA and symptom severity score to assess efficacy and ensure no increase in harm in the intervention arm.

**Yale will be the central data analysis site.** All data will be analyzed by a full time statistician at the Program of Applied Translational Research.

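### The final primary test has two alpha levels, 0.04 in the sample size and 0.05 in the analysis plan; after the p<0.01 interim stop, 0.05 gives about 5.8% two-sided type I error

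*Combined protocol and SAP*

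**What the plan says.** All the relevant text is current and most of it stands in Section 14 (Statistical Considerations).

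- **Sample size, primary outcome.** The trial is sized for "80% power (with a two-sided alpha level of 0.04 to detect an absolute reduction in hospital admission rates of 5% or more", giving 1362 patients, with 1500 to be enrolled to allow for 10% loss to follow-up.
- **Sample size, secondary outcomes.** A different level is used. For time to recovery, "a sample size of 196 would be required to provide 80% power (with a two-sided alpha level of 0.05"; the symptom score is also sized at 0.05.
- **Data analysis plan.** After naming Pearson's chi-square test for the primary outcome, it states: "The alpha level will be set at 0.05 for all analyses, 95% confidence intervals will be calculated, and all comparisons will be two-tailed".
- **Interim analysis.** "Once our enrollment target for the secondary outcomes is reached (n~200), we will perform an interim analysis to assess safety, feasibility and treatment effect". For the primary outcome the rule, under Stopping Rules in Section 11, is: "If there is a significant difference between the two arms with p-value of <0.01, we will not continue the study". Sections 13 and 14 repeat it. The Use of Placebo section describes the look as one for efficacy, with early termination if benefit is shown.

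The documents do not explain the 0.04, do not connect it with the 0.01 interim threshold, and do not exempt the final primary test from the general 0.05 rule.

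**The concern.** The threshold that decides whether a confirmatory trial has succeeded must be fixed once, before unblinding. Here the level that justified the sample size and the level given for the analysis differ. If the final p-value falls between 0.04 and 0.05, either answer can be defended from the text, so the choice could be made after the result is known.

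Read literally, the data analysis plan also places a full 0.05 test after an efficacy look at 0.01. Two chances of a positive finding, one of them already using the whole 5%, must take the overall error above 5%.

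**Working it through.** **Inputs.** From Section 14: admission rates 14% (placebo) and 9% (14% minus 5 points), 80% power, two-sided alpha 0.04 or 0.05, 1362 evaluable of 1500 enrolled, uncorrected Pearson chi-square, interim at about 200 with a stop at p<0.01. Assumed, because the documents do not say: 1:1 allocation, a two-sided interim p-value, outcomes known for about 200 patients at the interim, and a stop at p<0.01 counted as a positive result.

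**1. Reproduce the stated sample size.** Two proportions, pooled variance under the null, no continuity correction:

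n per arm = [z(1−α/2)·√(2·p̄·(1−p̄)) + z(0.80)·√(p₁(1−p₁) + p₂(1−p₂))]² / (p₁−p₂)²

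With p̄ = 0.115, the two square roots are √0.20355 = 0.4512 and √(0.1204 + 0.0819) = 0.4498.

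- α = 0.04: (2.054 × 0.4512 + 0.842 × 0.4498)² / 0.0025 = 681.3 per arm, 1362.7 in total. The plan states 1362.
- α = 0.05: (1.960 × 0.4512 + 0.842 × 0.4498)² / 0.0025 = 637.9 per arm, 1275.8 in total.

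At 681 per arm, power is 80.0% at 0.04 and 82.5% at 0.05. A continuity-corrected formula at 0.05 gives about 1355, which is near 1362. However, it contradicts the alpha printed in the same sentence and does not match the uncorrected test planned. The 0.04 is not a slip of the pen.

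**2. Overall type I error over the two looks.** With Z₁ the interim and Z₂ the final statistic, bivariate normal with correlation √(information fraction):

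error = 1 − P(|Z₁| < 2.576 and |Z₂| < c), where c = 1.960 for 0.05 and 2.054 for 0.04.

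| Interim fraction | Correlation | 0.01 then 0.05 | 0.01 then 0.04 |
|---|---|---|---|
| 200/1362 = 0.147 | 0.383 | 5.82% | 4.84% |
| 200/1500 = 0.133 | 0.365 | 5.83% | 4.86% |

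In the benefit direction alone the error is about 2.9% against 2.4%. The final level that gives exactly 5% overall is about 0.0415. Whatever the interim size, 0.01 + 0.04 = 0.05 bounds the second scheme at 5% (Bonferroni).

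**3. Simulation check.** Pearson chi-square trials, 100 per arm at the interim, 681 or 750 per arm at the end, 2,000,000 runs per setting, null event rates from 5% to 14%: about 5.7% to 5.9% for 0.01 then 0.05, and 4.7% to 4.9% for 0.01 then 0.04.

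**4. A result on which the two levels disagree.** With 681 per arm, take 95 admissions (13.95%) against 71 (10.43%), a difference of 3.52 points. Pearson's test gives p = 0.0468. The 95% Wald interval, 0.05 to 6.99 points, excludes zero; the 96% interval, −0.11 to 7.16 points, includes it.

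**The case against.** The best defence is that the plan already splits its alpha: 0.01 at the interim and 0.04 at the end add to 0.05, and the 0.05 in the data analysis plan is the overall level, written as a general closing sentence. That may well be the intent. But the sentence says all analyses and pairs the level with 95% intervals, and no text links 0.04 to the interim look. Even on this reading the sentence is wrong for the final primary test. What stands is that the split is an inference, which the sponsor should confirm.

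The inflation is also modest: about 0.8 points two-sided, about 0.4 in the benefit direction, and only final p-values between 0.04 and 0.05 are affected. The worked case was chosen to lie in that band and says nothing about how often it would arise. All of this is fair, but it does not remove the contradiction.

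Finally, the interim is triggered by enrolment, whereas the primary outcome needs a month of follow-up, so fewer than 200 outcomes may be known. If only 50 per arm were mature (an assumption), the discrete chi-square makes the interim look conservative and the overall error is about 5.3% at a 5% event rate, 5.5% at 7% to 9%, and 5.8% at 14%. A later look also lowers it: 5.5% at an information fraction of 0.5 and 5.02% at 0.9. The size therefore depends on maturity and event rate; the direction does not.

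**Conclusion.** The concern holds. The text gives two thresholds for the trial's main claim, and the one in the data analysis plan, taken with the p<0.01 interim stop, does not hold 5%. The overall two-sided error is about 5.8% with roughly 200 known outcomes at the interim, and 5.3% to 5.8% if only half of those are mature. The 0.04 level holds 5% in every case and is the level from which 1362 was calculated. The figures rest on 1:1 allocation, a two-sided interim test and counting an interim stop as a positive finding. The contradiction itself rests on no assumption. The cost of using 0.05 is type I error; power would in fact be slightly higher.

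**What to change.** In the Section 14 data analysis plan, replace the general alpha sentence with wording such as:

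> The final comparison of the primary outcome will be tested at a two-sided alpha of 0.04 with a 96% confidence interval, following the interim test at 0.01. All other analyses will use a two-sided alpha of 0.05 with 95% confidence intervals.

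The sponsor should confirm that 0.04 was meant as the level remaining after the interim look. Three smaller points can be settled in the same edit:

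- State that the adjusted logistic regression of the primary outcome is supportive, or give it the same 0.04 level, so that it does not sit beside the main test at a different threshold.
- The 96% interval is the one that agrees with a 0.04 test. If 95% is kept by convention, say that the decision rests on the p-value against 0.04.
- State whether interim results on the secondary outcomes are descriptive. Sections 13 and 14 now say they are analysed for efficacy, so this is a decision for the sponsor and is separate from the main correction.

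A final level of about 0.0415 would also hold 5%, but it would depend on the interim size and would not match the sample size calculation.

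The cost is a few sentences. No patients are added, and power remains 80.0% at 1362 evaluable; if 10% of 1500 are lost, 1350 remain and power is 79.6%. The change must be made before unblinding.

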***Responsibilities of protocol specific DSMC may include:***

- Reviewing the research protocol, and informed consent documents.
- Evaluating the progress of the study on an ongoing basis including periodic assessments of data quality, participant recruitment, accrual and retention, participant risk versus benefit, performance of study site(s), and other factors that can affect the outcome.
- Considering the impact of factors external to the study when new information, such as scientific or therapeutic developments becomes available that may affect safety of participants, their willingness to participate in the study or the ethics and conduct of the study.
- Reviewing UPIRSO, SAE, AE, and protocol deviation reports.
- Reporting any problems with study conduct or performance to the IRB.
- Ensuring the measures to ensure the confidentiality of study data and results are appropriate.
- Reviewing and evaluating requests for protocol modifications/amendments.
- Reviewing before study initiation the stopping rules and plans for interim analyses presented in the protocol. These plans outline the conditions under which a study may be stopped (e.g., difficulties in recruitment, retention, obtaining outcome measures or other issues).
- Reviewing the interim analyses and/or accumulating data at the specified interval(s), and as appropriate and make a recommendation to continue, terminate or modify the study based on observed benefit or harm in accordance with the planned stopping rules.

**Section 12.** For multi-site studies for which the Yale PI serves as the lead investigator: How will adverse events and unanticipated problems involving risks to subjects or others be reported, reviewed and managed?

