## Use of Placebo:

**If use of a placebo is planned, provide a justification which addresses the following:**

- a) Describe the safety and efficacy of other available therapies. If there are no other available therapies, state this. As there are no current treatments for COVID-19, there is no other safe or efficacious therapy that we can use instead of placebo.
- b) State the maximum total length of time a participant may receive placebo while on the study.  
14 days.
- c) Address the greatest potential harm that may come to a participant as a result of receiving placebo.  
There should be no harm incurred by participants receiving placebo, which is corn starch (non-resistant digestible starch).
- d) Describe the procedures that are in place to safeguard participants receiving placebo.  
We will perform interim analysis for efficacy to determine if early study termination may be needed if there is evidence of benefit in the intervention arm that precludes us to continue the study ethically.

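### One direction-blind p<0.01 stopping rule at about 13% of the information serves both benefit and harm poorly; separate thresholds would cost only wording

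*Combined protocol and SAP*

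**What the plan says.** The Stopping Rules section contains one criterion: "If there is a significant difference between the two arms with p-value of <0.01, we will not continue the study". Interim analysis 3 in Sections 13 and 14 repeats it: "If there is a significant difference between the two arm with p-value of <0.01, we will not continue the study". None of the three places gives a direction, and the data analysis plan in Section 14 makes every comparison two-tailed.

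The look is timed by the sample size for the secondary outcomes, not by information on hospitalization: "Once our enrollment target for the secondary outcomes is reached (n~200), we will perform an interim analysis". The Use of Placebo section presents it as a check for benefit: "We will perform interim analysis for efficacy to determine if early study termination may be needed if there is evidence of benefit". Among the DSMC's possible responsibilities is a recommendation to continue, "terminate or modify the study based on observed benefit or harm in accordance with the planned stopping rules".

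The sample-size paragraph in Section 14 reads "Assuming a 14% admission rate in the placebo group, we calculated that a sample size of 1362" and uses a two-sided level of 0.04, 80% power and a 5-point reduction; "we will enroll 1500 to account for 10% loss to follow up". The data analysis plan, a few lines later, sets the level at 0.05 for all analyses. No second look at hospitalization is scheduled.

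**The concern.** Evidence that justifies ending a phase III trial early for benefit should be strong, because the resulting estimate must stand alone. Evidence that prompts a safety committee to reconsider an apparent excess of admissions need not be as strong. A single symmetric p<0.01 treats both alike.

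At so early a look, three things are at stake. A benefit stop would rest on few events and an inflated estimate. The 0.01 reserved for the look comes out of the final test. A moderate excess of admissions on RPS would seldom reach the only stated threshold.

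**Working it through.** **Inputs.** From Section 14: 14% versus 9%, two-sided 0.04, 80% power, 1362 evaluable, 1500 enrolled, Pearson chi-square, look at about 200. From the primary outcome definition: hospitalization in the first month. Assumptions: 1:1 allocation (no ratio is stated) and 100 complete outcomes per arm at the look.

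**1. The plan's own sample size.** With mean rate 0.115, n per arm = [z(0.98)·√(2·0.115·0.885) + z(0.80)·√(0.14·0.86 + 0.09·0.91)]² / 0.05² = [2.054·0.4512 + 0.8416·0.4498]² / 0.0025 = 681.3. This rounds up to 682, or 1364 in total, against the stated 1362. At 0.05 the total would be 1276, so 0.04 is the level actually used.

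**2. Information at the look.** 200/1500 = 13.3% (200/1362 = 14.7% of the evaluable number). Expected admissions are 100·(0.14 + 0.09) = 23, against 681·0.23 = 157 at the end. These are upper figures, because enrollment triggers the look and the outcome takes a month. If 1500 enroll evenly over the six-month administration and data-collection period (an assumption, 250 per month), the 200th enters at 0.8 month, when essentially no one has a complete outcome.

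**3. Overall type I error.** The interim and final statistics are bivariate normal with correlation √0.133 = 0.365, and overall alpha = 1 − P(|Z1|<c1, |Z2|<c2).

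| Interim level | Final level | Overall alpha |
|---|---|---|
| 0.01 | 0.04 | 0.0486 |
| 0.01 | 0.05 | 0.058 |
| 0.001 | 0.049 | 0.0498 |
| 0.001 | 0.05 | 0.0508 |

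After a 0.01 look, the final level that keeps 0.05 overall is 0.0415.

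**4. Benefit boundary.** With 14/100 on placebo, 3/100 on RPS gives z = 0.11/√(2·0.085·0.915/100) = 2.79, p = 0.005, difference 11 points (95% CI 3.4 to 18.6). Four on RPS gives p = 0.013 and does not stop. Exact binomial enumeration of the chi-square test under 14% versus 9% gives:

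| Two-sided threshold | P(stop for benefit) | Mean observed reduction given a stop | Mean admissions given a stop |
|---|---|---|---|
| 0.01 | 6.7% | 13.6 points | about 24 |
| 0.001 | 1.2% | 16.3 points | about 24 |

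With 14% in both arms, the 0.01 rule stops for benefit in 0.5% of trials.

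**5. Power.** For the final test at 681 per arm, power is 80.0% at 0.04, 80.4% at 0.0415 and 82.3% at 0.049. For 80% power at 0.049 the total is 1284 instead of 1364, a difference of 80. Simulation that also counts interim rejections gives about 80.5% for 0.01 then 0.04 and 82.6% for 0.001 then 0.049, a gain of about 2 points.

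**6. Harm boundary.** With 14/100 on placebo, 28 on RPS gives z = 0.14/√(2·0.21·0.79/100) = 2.43, p = 0.015, so a doubling does not trigger the rule; 29 gives p = 0.0098 and does. The true RPS rates below are illustrative assumptions against 14% on placebo.

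| True RPS rate | Current p<0.01 rule fires (harm) | One-sided p<0.05 guideline fires |
|---|---|---|
| 17% | 2% | 14% |
| 19% | 5% | 24% |
| 21% | 10% | 36% |
| 28% | 45% | 79% |

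The one-sided guideline fires in 5% of trials if RPS has no effect and in 0.3% at the planned benefit.

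**The case against.** **The 0.01 is already budgeted.** The trial is sized at 0.04, and 0.01 followed by 0.04 gives 0.0486 overall with the stated 80% power. This stands. A reader might infer that the interim rule by itself inflates the false-positive rate; it does not. Inflation to 0.058 arises only if the final test follows the data analysis plan's 0.05. The power figure is likewise a gain forgone, not a shortfall.

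**The look has an ethical purpose.** The Use of Placebo section offers it as a safeguard for placebo participants, and a stricter threshold nearly removes the chance of using it. This also stands, as the main cost of the change. A stop at p<0.001 would carry an even more inflated estimate (16.3 points); the change makes such stops rarer, not more accurate.

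**This rule is not the only route to stopping.** Inpatient hospitalization is defined as a serious adverse event. The site principal investigators review safety weekly, and they or the IRB may stop the study. The DSMC meets monthly, receives quarterly event tables and can hold ad hoc reviews. Interim analysis 1 lets it advise on recruitment without a p-value. A reader might infer that a real excess of admissions would pass the look and that the remaining 1300 would simply be enrolled. The documents do not support that. What remains is that none of these routes sets a threshold for admissions by arm, the listed DSMC report contents do not mention tables by arm, and the benefit-or-harm item in the DSMC's list refers back to the planned stopping rules.

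**Nothing in the documents suggests that RPS raises admissions.** Prior use is described as having minimal adverse events and no serious ones. The harm rates above therefore show how the rule behaves and predict nothing.

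**Conclusion.** The concern holds as a cheap improvement, not as a validity failure. One undirected p<0.01 rule, at no more than about 13 to 15% of the information, rarely stops for benefit under the planned effect (6.7%). When it does stop, it overstates the effect (13.6 points against 5). It also detects moderate harm poorly (10% at an assumed 21% RPS rate). Moving to separate thresholds gains about 2 points of power and adds harm guidance that costs no alpha.

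A reader might take the 14-versus-3 boundary to mean that a benefit stop would rest on 17 admissions. That is one example; the average given a stop is about 24.

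The conflict between 0.04 and 0.05 needs resolving in any case. The magnitudes assume 1:1 allocation and 100 complete outcomes per arm. If the look is run at enrollment of the 200th participant, less information will be available.

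**What to change.** Amend the Stopping Rules section, Interim analysis 3 in Sections 13 and 14, and the sample-size and data analysis paragraphs of Section 14 together:

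1. **Benefit.** Stop only at two-sided p<0.001 and test the primary outcome finally at two-sided 0.049 (overall 0.0498). Change both the 0.04 in the sample-size paragraph and the 0.05 for all analyses in the data analysis plan to match.
2. **Harm.** Add a separate, non-binding guideline, for example one-sided p<0.05 toward more admissions on RPS, that triggers a DSMC review of continuation. Exempt it from the two-tailed statement. Being non-binding and directed at harm, it leaves the final alpha unchanged. It improves detection of moderate harm but does not ensure it: 36% at an assumed 21%.
3. **Timing.** Run the look when about 200 participants have complete one-month outcomes, replacing the trigger "Once our enrollment target for the secondary outcomes is reached (n~200").

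The cost is wording only; no participants or procedures are added. The downsides are that the chance of an early benefit stop under the planned effect falls from 6.7% to 1.2%, any such stop would still overstate the effect, and there is a 5% chance of a needless harm review if RPS has no effect.
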